1.0 Research Design

1.1 Purpose/Specific Aims

The study will refine the algorithms that operationalize on-task behavior and the process of displaying participant performance within the virtual reality (VR) environment, then conduct trials to examine said intervention. We will collect data on feasibility, usability and key mechanisms of action, concentration, motivation, and effort/efficiency. A randomized control trial will be implemented to evaluate the effects of the distraction free VR environment alone and combined with automated contingency management and moderators and mediators of outcomes.

A. Objectives

1. Refine objective virtual reality (VR) data capture techniques, including keyboard and mouse click algorithms, eye gaze tracking, and screenshot capturing.
2. Develop and refine contingency management algorithms and conduct focus groups to determine ways to improve feasibility/usability.
3. Pilot test the feasibility/usability of the VR environment and evaluate impact on target mechanisms.
4. Conduct a parallel group randomized trial with college students with ADHD randomized to 1 of 3 groups: (1) VR environment alone, (2) VR + contingency management or (3) a pass-through VR.

B. Hypotheses / Research Question(s)

Data will inform the use of virtual reality to support the academic performance and mental health of individuals with ADHD. The VR intervention will target specific mechanisms of concentration, homework effort, and homework motivation. Trial data will demonstrate the feasibility/usability of the VR system and associated algorithms to monitor attention and focus in VR.

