1.3 Research Design and Methods

The study will take place in 4 phases, each utilizing methodology specific to the phase. Phases are created to improve clarity of expectations for participants entering at different points in the study and clarity of the general research protocol.

- PHASE 1: Refine objective data capture techniques. Key to any VR intervention is the ability to monitor and quantify work productivity behaviors and to establish an accurate baseline. This has been done with adult workers, but we will need to refine the keyboard and mouse click algorithms for use with emerging adults (aged 18-25 years) with ADHD who are completing real homework assignments and studying (n=30 to complete the phase). The study design for this phase will follow an AABBAABB design – where A is passthrough control and B is the immersive VR environment. In this way, each participant essentially serves as their own control as they switch between passthrough and VR immersion sessions. The team will also explore whether adding in eye gaze tracking and periodic screenshots improves the accuracy of the algorithms.
- PHASE 2: Develop and refine contingency management algorithms. Once data capture capabilities have been confirmed in emerging adults with ADHD, we must test the ability to combine these data into an algorithm to provide real-time performance feedback to participants and contingency management (n=30 to complete the phase). As with Phase 1, the study design for this phase will follow an AABBAABB type design – where A is passthrough control and B is the immersive VR environment. In this way, each participant essentially serves as their own control as they switch between passthrough and VR immersion sessions. The team will also conduct focus groups to determine ways to improve feasibility/usability and to identify strategies and tools that motivate participants to complete work.
- PHASE 3: Pilot test and evaluate impact on target mechanisms. Conduct a small randomized control trial (RCT) to assess the feasibility/usability and preliminary effects of the VR environment alone (n=15) compared to VR environment + contingency management (n=15) and the VR passthrough control (n=15). Proposed mechanisms of action will be measured every session,

including algorithm data plus self-ratings of concentration, homework effort, and homework motivation.

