- **PHASE 4: Conduct a parallel group randomized trial.** Randomize 252 college students with ADHD to: (1) VR environment alone, (2) VR + contingency management or (3) a pass-through VR headset for 6 weeks. Assess target mechanisms at each session and collect ratings of functioning at baseline, intervention outcome and at a 3-month follow-up to facilitate evaluation of efficacy, dose, moderation, and mediation.

All visits will be conducted at participants' homes and the LSU or Rutgers library, [name] lab at Louisiana State University, or via HIPAA-compliant videoconferencing (e.g., Zoom). Trained study staff will be on-site and available to assist at all times.

A. Research Procedures

This study is taking place at two sites, Rutgers and Louisiana State University (LSU). Rutgers is the "Psychology site" and the PI is a licensed clinical psychologist, and LSU is the "Engineering/VR site" and the PI is in Computer Science. As such, all participant consenting, inclusion/exclusion evaluations, and outcome assessments are handled by the Rutgers site. These portions will be done virtually, via REDCap surveys and teleconference. Approximately half of the participants will be enrolled and use VR at the Rutgers site and half at the LSU site. The scheduling and implementation of the VR sessions is handled by the site/university where participants are located. All data are collected via REDCap and stored at the Rutgers site only. The only exception is the data captured by the VR (keyboard and mouse click data, eye gaze, and screenshot captures), which is maintained and analyzed at LSU.

For the VR intervention provided in each phase, participants will be provided the option of using the VR headset while completing homework and studying either in their rooms/homes or at the library, and at a consistent time each day to help control for natural variations in focus due to chronobiological sleep/wake preferences.

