complete the BAARS-Self survey. To evaluate other services and treatments the participants may be receiving, they will complete the Service Utilization for College student's questionnaire. To measure treatment moderators and outcomes, they will complete the RCADS, Columbia Suicide Severity Index (required by NIMH), BDEFS, BAI-2, ADHD Impact Model-Adult (AIM-A), and surveys on Academic Record (GPA & Percentage of Assignments Completed), and a Reading Comprehension Standardized Assessment. Questions on feasibility and usability of the VR system will be asked. Outcome assessments will be performed by Rutgers study staff using Rutgers-hosted REDCap. Additionally, only for Phase 1 as part of the pilot process, participants will be asked to conduct a brief 15-min follow-up phone interview with a member of the research team to further elaborate on their questionnaire responses regarding their experiences with the virtual reality headset, the virtual study environment, and any issues they encountered while using the technology. This will provide valuable qualitative information for the LSU VR developer team to then improve the system for future phases of the study.

PHASE 2: Develop and refine contingency management algorithms.

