- Columbia Suicide Severity Index

- BDEFS
- BAI-2
- ADHD Impact Model-Adult (AIM-A)
- Academic Records (Homework completion & grades; self-report only)
- GPA & Percentage of Assignments Completed (Homework completion & grades; self-report only)
- Reading Comprehension Standardized Assessment
- ADHD Rating Scale-Parent (childhood; completed by parent or other reporter)
- SCID-V RV
- Parent Contact Form

Each of 10 sessions:

- Key strokes and mouse clicks
- Eye tracking
- Periodic screenshots of participant screens
- 10-item Systems Usability Scale
- Adult Concentration Inventory
- Homework Motivation Index
- Homework Effort Index
- Current Day Medication Adherence

Outcome Assessment:

- Service Utilization for College Students
- Current Day Medication Adherence survey
- BAARS-Self
- RCADS
- Columbia Suicide Severity Index
- BDEFS
- BAI-2
- ADHD Impact Model-Adult (AIM-A)
- Academic Record (GPA & Percentage of Assignments Completed)
- Reading Comprehension Standardized Assessment
- Feasibility and usability of the VR systems

PHASE 2: Develop and refine contingency management algorithms.

Initial evaluation:

- Contact, demographic, and background information
- Service Utilization for College Students
- Current Day Medication Adherence survey
- BAARS-Self
- Pre-screening questions
- Adult Concentration Index (ACI)
- RCADS

- Columbia Suicide Severity Index
- BDEFS
- BAI-2
- ADHD Impact Model-Adult (AIM-A)
- Academic Record (GPA & Percentage of Assignments Completed)
- Reading Comprehension Standardized Assessment
- ADHD Rating Scale-Parent (childhood)
- SCID-V RV
- Parent Contact Form

Each of 10 sessions:

- Key strokes and mouse clicks
- Eye tracking
- Periodic screenshots of participant screens
- 10-item Systems Usability Scale
- Adult Concentration Inventory
- Homework Motivation Index
- Homework Effort Index
- Current Day Medication Adherence

Outcome Assessment:

- Service Utilization for College Students
- Current Day Medication Adherence survey
- BAARS-Self
- RCADS
- Columbia Suicide Severity Index
- BDEFS
- BAI-2
- ADHD Impact Model-Adult (AIM-A)
- Academic Record (GPA & Percentage of Assignments Completed)
- Reading Comprehension Standardized Assessment
- Feasibility and usability of the VR systems

Focus Group

- VR Study Focus Group Questions

PHASE 3: Pilot test and evaluate impact on target mechanisms.

And

PHASE 4: Conduct a parallel group randomized trial.

Initial evaluation:

- Contact, demographic, and background information

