1.9 Data Collection

A. Primary Data Collection

- Location: Assessments (initial evaluation, outcome visit) and focus groups will be completed via HIPAA-compliant videoconference (e.g., Zoom) with the Rutgers study staff. Electronic questionnaires will be sent directly via secure web-based survey sites (e.g., REDCap). Intervention visits will be completed at participants' homes or the LSU/Rutgers library.
- Process of Data Collection: Diagnostic assessments and intervention sessions will be completed by graduate students enrolled in masters or doctoral psychology programs, post-baccalaureate research assistants who have received specialized training, or post-doctoral

fellows. The VR intervention will be supervised by [name] and the diagnostic assessments will be supervised by [name].

- **Timing and Frequency:** Phases will occur in chronological order, with one completing before the next begins. See sections 1.3 C and 1.10 for more information on timing.
- **Procedures for Audio/Visual Recording:** Audio of the focus groups in Phase 2 will be recorded. No other audio/visual data are being collected.
- **Study Instruments:**
 - PUBLISHED
 - SCID-V RV (First et al., 2015)
 - Service Utilization for College Students (Anastopoulos et al., 2018)
 - BAARS-Self (Barkley, 2011a)
 - ADHD Rating Scale – Parent (childhood; DuPaul et al., 2016)
 - Adult Concentration Index (ACI; Fredrick et al., 2021)
 - Homework Motivation Index (Martin, 2001)
 - Homework Effort Index (Trautwein et al., 2006)
 - RCADS (Ebetsutani et al., 2010)
 - Columbia Suicide Severity Index (Posner et al., 2011)
 - BDEFS (Barkley et al., 2011b)
 - BAI-2 (Steer et al., 1997)
 - ADHD Impact Module-Adult (AIM-A; HealthAct, 2007)
 - Systems Usability Scale (Brooke, 1996)
 - GAD-7 (Spitzer et al., 2006)
 - PHQ-9 (Kroenke et al., 2001)
 - BFIS (Barkeley, 2011c)
 - UNPUBLISHED
 - Demographic and Background
 - Current Day Medication Adherence
 - Academic Record (GPA & Percent of Assignments Completed)
 - Reading Comprehension Standardized Assessment
 - Parent Contact Form
 - Subject Contact Form
 - Pre-screening questions
 - WHODAS (Required by NIMH/NDA)
 - DSM-5 Level 1 Cross-Cutting Symptom Measure (Required by NIMH/NDA)

- **Ethnographic Studies, Interviews, Or Observation:** N/A

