analyzed using MPlus will address missing data using full information maximum likelihood estimates. This approach makes full use of available data and is one of several procedures considered the state of the art for addressing missing data.

Intent to Treat Analysis: An intent-to-treat approach will be used to analyze the data, wherein each participant will be kept in the group to which they were randomized for analysis, regardless of treatment compliance. A mixed-effects model will be used to account for the repeated-measure nature of the study design. Time will be treated as a dummy-coded categorical variable using baseline as the reference. A student-level random effect will be included and modeled using an auto-regressive covariance structure to account for within-subject dependence due to repeated measurements. The models will also include treatment condition as a student-level fixed effect, and condition x time interaction effects. This modeling will allow us to compare baseline to 8-week (post) changes, and the extent to which these changes differ across conditions.

Mediator Analyses: Mediational analyses will be conducted using structural equation modeling. There are advantages of a structural equation modeling approach to estimating and determining the significance of indirect effects within mediational models and outlined specific estimation procedures that are available in MPlus. All analyses will be conducted in MPlus which provides estimates that partition the total effect of an independent variable on a dependent variable into the direct and indirect effects using bootstrap estimation procedures. Preliminary analyses will be conducted separately for each mediator. Scores on the mediator will be modeled as a function of pretest scores on the mediator, intervention condition, and covariates. The intervention's effect can then be partitioned into the direct effect on changes (e.g., on school grades) at posttest and follow-ups and the indirect effects via the mediator. These initial analyses will be used to guide a more comprehensive model that will incorporate mediators that emerge as significant within the individual models. Primary mediation analyses will focus on whether change in the proposed mechanisms of action mediates improvement in AIM total scores and BDEFS.

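### AIM total score is named as a primary mediation outcome for Phase 4, but no Phase 3 or 4 assessment collects it

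*Combined protocol and SAP*

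**What the plan says.** Mediation is part of what the randomized trial is for. Section 1.1 says it will evaluate the VR environment alone and combined with "automated contingency management and moderators and mediators of outcomes". The Phase 4 overview in section 1.3 says the trial will "collect ratings of functioning at baseline, intervention outcome and at a 3-month follow-up to facilitate evaluation of efficacy, dose, moderation, and mediation". The Phase 3 overview gives the mechanisms measured at every session, "including algorithm data plus self-ratings of concentration, homework effort, and homework motivation".

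Section 6.1, in the Mediator Analyses paragraph of its Phase 4 text, then fixes the outcomes: "Primary mediation analyses will focus on whether change in the proposed mechanisms of action mediates improvement in AIM total scores and BDEFS". The same paragraph gives one other outcome by way of example, where the intervention effect is "partitioned into the direct effect on changes (e.g., on school grades) at posttest and follow-ups". Missing data in these Mplus models are to be handled by full information maximum likelihood.

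The AIM instrument appears in the Phase 1 outcome assessment, where "they will complete the RCADS, Columbia Suicide Severity Index (required by NIMH), BDEFS, BAI-2, ADHD Impact Model-Adult (AIM-A), and surveys on Academic Record". The Phase 2 outcome text repeats it. Section 1.9 A lists "ADHD Impact Module-Adult" among the published instruments without assigning it to a phase.

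**The concern.** The analysis text and the assessment schedule do not match. An outcome named for the primary mediation analyses has to be measured in the trial being analysed, at baseline and afterwards, because the analysis concerns improvement. If the AIM-A is not given in Phase 4, half of the named primary mediation analysis has no data.

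The plan has no rule for replacing an outcome. Several other measures are collected at all three time points, so whoever runs the analysis would have to drop the AIM half or choose a substitute. If that choice is made once results can be seen, the word primary no longer protects against selection. Nothing in the document shows that this has happened; the risk is still avoidable.

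**Working it through.** The plan has no figure to reproduce here. The check compares section 6.1 with every place that schedules assessments.

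**Data-point lists, section 1.3 B**

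| List | AIM-A | BDEFS |
|---|---|---|
| Phase 1 initial | yes | yes |
| Phase 1 outcome | yes | yes |
| Phase 2 initial | yes | yes |
| Phase 2 outcome | yes | yes |
| Phases 3/4 initial | no | Short Form |
| Phases 3/4 outcome | no | Short Form |
| Phases 3/4 3-month | no | Short Form |
| Session lists, every phase | no | no |

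Counting assessment lists only, the AIM-A is in 4 of 4 for Phases 1 and 2 and in 0 of 3 for Phases 3 and 4. Adding the Phase 3/4 session list makes it 0 of 4. BAARS-Self, BDEFS Short Form, BFIS and the Academic Record are each in 3 of 3.

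**Narrative, section 1.3 A**

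- The initial-evaluation text names BDEFS and BFIS, not AIM-A.
- The measures it adds for Phase 4 are the DSM-5 Cross-Cutting measure and the WHODAS.
- The Phase 3 outcome battery is itemised as BAARS-Self, BDEFS, BFIS and the academic measures. Follow-up repeats that battery.
- Phase 4 takes over the Phase 3 procedures, apart from the number randomized.

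Lists and narrative agree, so this is not a single dropped bullet.

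**Can the data come from elsewhere?**

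- No other instrument abbreviated AIM is defined.
- Phases 1 and 2 have no randomized arms, so their AIM-A scores cannot stand in.
- Full information maximum likelihood uses the observed part of a variable together with its observed relations to other variables. With no AIM score in any Phase 4 participant there is no observed part, and no path to AIM can be estimated.

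**Size**

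One of two named outcomes is affected. As an illustration, pair each of the four mechanisms (algorithm data, concentration, effort, motivation) with each named outcome: 4 × 2 = 8 single-mediator models, of which 4 × 1 = 4 have no outcome data. With the three self-rated mechanisms only, the count is 3 of 6.

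**Side point: the label for the post visit**

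The Intent to Treat paragraph of section 6.1 labels the post assessment as 8 weeks. The Phase 4 line of section 1.3 C, counted from initial evaluation, puts the last session at 1 + 1 + 2 = week 4 and the end of the outcome week at 4 + 1 = week 5, which is 8 − 5 = 3 weeks earlier unless make-up time is added. The stated Phase 4 periods also differ:

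- 6 weeks (section 1.3 overview);
- ten headset sessions over three weeks after the baseline sessions (section 1.3 A, carried over from Phase 3);
- one baseline week plus two weeks (section 1.3 C);
- all 12 sessions within three weeks (section 4.6 B).

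Section 6.1 does not say where its count starts. With the 6-week figure, 1 + 1 + 6 = 8, so the source of the label cannot be determined. The mixed model is unaffected, because time is categorical and an outcome assessment follows session 12.

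**The case against.** The strongest reply is that the document shows a conflict, not which side of it is out of date. The Phase 3/4 data-point list has slips of its own: it refers to 10 sessions where section 1.3 A gives 12, and it places the usability scale at sessions 4 and 10 where section 1.3 A says 4 and 12. The AIM-A is still on the study-wide instrument list. So the exact statement is that no AIM-A collection is scheduled for Phase 4. That qualification stands, but it does not rescue the analysis, because the section 1.3 A narrative omits the AIM-A as well and the instrument list is explained by its use in Phases 1 and 2.

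A second reply is that the model count proves little. Section 6.1 treats the separate-mediator models as preliminary, and the count ignores the three-arm contrasts and the several time points. That is fair. The count is only an illustration, and the conclusion rests on one of two named outcomes.

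A third reply concerns importance. These are the primary analyses of the mediation aim, not the primary analysis of the trial. AIM and BDEFS are not declared the only mediation outcomes, since school grades are mentioned too. All of this stands and limits the reach of the point. It does not remove the mismatch.

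**Conclusion.** The point holds, with high confidence. As written, the AIM half of the Phase 4 primary mediation analyses cannot be run: one of its two named outcomes is scheduled at none of the three Phase 4 assessments. The BDEFS half can be run, although section 6.1 does not say that Phase 4 uses the Short Form. The between-arm comparisons on the section 1.6 outcomes and the justification of 252 participants do not depend on AIM.

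The conclusion assumes that AIM in section 6.1 means the AIM-A and that Phase 4 follows its written schedule. The BFIS appears in the Phase 3/4 lists, from which the AIM-A is absent, so section 6.1 may simply not have been updated after a change of battery. That is an inference; the document does not say so. It should be fixed before Phase 4 outcome data are examined.

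**What to change.** Replace AIM total scores in section 6.1 with a named outcome collected at baseline, outcome and 3 months, and date the change before any Phase 4 outcome data are examined. On scheduling alone, the BFIS and the Academic Record (GPA or percentage of assignments completed) qualify; so does the BAARS-Self. The sponsor must confirm that the chosen measure suits the mediation question. For the Academic Record this includes the period each report covers, which the document does not give. State in the same sentence that BDEFS means the Short Form. The cost is wording only.

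Alternatively, if Phase 4 enrolment has not begun, add the AIM-A to all three Phase 4 assessments. This lengthens an initial evaluation of about 1.5 hours, an outcome assessment of about 30 minutes and a follow-up of about 20 minutes (section 1.3 C); the AIM-A completion time is not given. If it were added later, each cohort already past baseline would have no baseline score, and one cohort is 63/252 = 25% of the sample (section 1.10).

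As a minor correction, define the post time point in section 6.1 as the outcome assessment after session 12, and reconcile the intervention periods in sections 1.3, 4.6 B and 6.1. This review does not say which period is right.

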6.2 Data Security

Data collection and entry will be done using REDCap (Research Electronic Data Capture). REDCap is a secure, web-based application designed exclusively to support data capture for research studies. REDCap provides: 1) an intuitive interface for data entry (with data validation); 2) audit trails for tracking data manipulation and export procedures; 3) automated export procedures for seamless data downloads to common statistical packages (SPSS, SAS, Stata, R); 4) procedures for importing data from external sources; and 5) advanced features, such as

branching logic and calculated fields. REDCap is approved by Rutgers as an electronic data capture (EDC) tool to collect and manage sensitive data. Per Rutgers regulations, only faculty, staff and sponsored students and affiliates may be granted access to REDCap Database. Application level security includes project level user permissions, event logging, and de-identification capabilities which facilitate the export and exchange of data in a coded manner. All REDCap data are stored on university database servers, which are backed-up and maintained following best practices. REDCap will be managing the system that supports this project, the study staff will be responsible for identifiable data collection, management, user rights, determining who has access and all logistics related to data collection and reporting.

There are safeguards in place to prevent accidental or inappropriate release of information. All staff are CITI and REDCap trained and supervised on how to handle confidential data. All identifiable information will only be saved on an approved secure server (the server is HIPAA compliant for security set up, the shared folder will only be browseable and accessible by the authorized person, each authorized person has their own account to log on server through Web VPN then work on the shared folder). The key will be password protected. Only the PIs and main study coordinator will know the password.

De-identified data are stored on both the approved secure server (only available to staff) and stored in a password protected shared drive (e.g., Rutgers-hosted Microsoft OneDrive). The shared drive will only be accessible to study staff and approved investigators. All data located on the drive is password protected. For example, participant inclusion/exclusion evaluation reports require a password to open. Only the study coordinator and MPI ([name]) who prepare the reports have access to the password. In addition, staffs' hard drives are encrypted using encryption software. Encryption software provides a comprehensive Data Protection Platform to control, manage and protect laptops, desktops and self-encrypting drives.

Precautions used to maintain the confidentiality of identifiable information: Standard practices are used to protect participant confidentiality and personal health information, including removing identifiers from all data collected, using only numbers to identify participant data, and keeping all data files when not in use in a locked filing cabinet behind a locked office. No names or other identifiers are used in computerized data files. REDCap, the survey tool that will be utilized for this project, has many security measures in place to prevent against inappropriate release of survey data and information. REDCap will be used to contact participants via email, collect survey responses, and record survey completion. To provide an additional layer of protection to participants, the collection of direct identifiers will be assessed separately from the general survey(s). The portable laptops that the research assistants use are only for transmitting data. The REDCap database is password protected. The laptops have no data stored on them, except the temporary file while the browser is open. All REDCap and OneDrive transmissions (to and from) are encrypted.

Per Rutgers IRB policy, data will be stored on the systems identified above for 6 years.

